12.1 Determination of Sample Size

A sample size of approximately 10 to 14 subjects per arm (approximately 40 to 56 total) is considered sufficient to characterize the PK, safety and preliminary efficacy of ACER-801 based on study results from a dual neurokinin 1,3 receptor antagonists in postmenopausal women (Trower et. al, 2020).

12.2 Analysis Populations

- The PK Population includes all randomized subjects who have evaluable PK samples.
- The Safety Population includes all randomized subjects receiving at least 1 dose of study treatment.
- The Modified Intent-to-Treat (mITT) Population includes all randomized subjects who receive study treatment with baseline and at least one post-baseline efficacy measurements.
- The Per-Protocol population includes all randomized subjects with baseline and efficacy measurement endpoint visits without any major protocol deviations that would have an impact on the efficacy measurements.

12.3 Primary Endpoints

12.3.1 Pharmacokinetic Endpoints

The pharmacokinetic endpoints are:

- C_{max} , t_{max} , AUC_{last} , AUC_{inf} , $AUC\tau$, Accumulation Ratio for C_{max} (AR_{Cmax}), Accumulation Ratio for AUC (AR_{AUC}), Metabolite Ratio of C_{max} (MR_{Cmax}), Metabolite Ratio of AUC (MR_{AUC}), $t_{1/2}$ of ACER-801 and its metabolite

12.3.2 Safety Endpoints

Safety endpoints are:

- Clinically significant changes in physical examination findings at Week 2 relative to Baseline
- Clinically significant changes in clinical laboratory evaluations (hematology, coagulation, serum chemistry, urinalysis, hormones, bone density markers) during the 2-week treatment period relative to Baseline
- Adverse events $\geq 5\%$
- All SAEs and discontinuations

12.4 Secondary Endpoints

The secondary endpoints are:

- Change in frequency of vasomotor symptoms at Week 1 and Week 2 relative to Baseline
- Change in severity of vasomotor symptoms at Week 1 and Week 2 relative to Baseline
- Change in hot flash severity score at Week 1 and Week 2 relative to Baseline

12.5 Exploratory Endpoints

The exploratory endpoints are:

12.5.1 Assessment of Hormone Changes

- The change in clinical laboratory assessments from Baseline for LH, FSH, estradiol, testosterone, SHBG, ACTH, cortisol, TSH, T3 (Total and Free) and T4 (Total and Free), will be assessed. Summary statistics of changes in the hormone levels relative to baseline will be generated.

12.5.2 Night-Time Awakenings

- The change in the number of NTAs throughout the study will be assessed.

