3.3 Exploratory Objectives

The exploratory objectives are to evaluate:

- The effect of ACER-801 at different doses on change in hormones compared to placebo including:
 - luteinizing hormone (LH)
 - follicle stimulating hormone (FSH)
 - estradiol
 - testosterone
 - sex hormone binding globulin (SHBG)
 - adrenocorticotropic hormone (ACTH)
 - cortisol
 - thyroid-stimulating hormone (TSH)
 - Triiodothyronine (T3) (Total and Free)
 - Thyroxine (T4) (Total and Free)
- Changes in the number night-time awakenings (NTA)
- Change in blood bone density marker concentration
- Changes in blood markers associated with stress
- Change in electrocardiogram (ECG) variables (heart rate, RR, PR, QRS, QT, QTcF, and QTcB)
- The relationship between PK exposure and measures of efficacy and/or safety

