10 EFFICACY ASSESSMENTS

Subjects will record VMS, including NTA, in a continuous hot flash diary during the Screening Period (2 weeks prior to Day -1) to assess eligibility. During confinement subjects will record VMS using a continuous hot flash diary. A description of the methods for VMS assessments is described in Sections 10.1 and 10.2.

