11.3.6 Mortara Surveyor for Electrocardiographs

A Mortara Surveyor will be used to collect ECG information (in triplicate) at timepoints coinciding with PK Samples. The extracted ECGs will then be blindly reviewed at a later time by an ECG core laboratory reader to determine changes in ECG variables (heart rate, RR, PR, QRS, QT, QTcF and QTcB). Graphical representations between ECG variables (e.g., QTcF) and plasma concentrations of ACER-801 and its metabolite will be generated.

The time and duration of ECG collection must be identical on Day -1, Day 1, and Day 14 and must be planned in relation to predose and 15 hrs postdose PK time points.

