12.5.3 Assessment of Changes in Blood Markers Associated with Stress

- The change from Baseline to Week 2 in catecholamines, vasopressin, gonadotropins, prolactin, and insulin.

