12.5.4 Markers of Bone Density

- The change from Baseline in bone density makers, including BSAP, osteocalcin, CTX, and P1NP will be summarized.

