12.6.4 Exploratory Analyses

The exploratory analyses will include summary statistics.

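### Exploratory endpoints are planned as change summaries and graphs with no active-minus-placebo estimate or interval, so NTA changes may carry a setting effect and no QTc effect size can be excluded

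*Combined protocol and SAP*

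**What the plan says.** Section 3.3 words the hormone objective as "The effect of ACER-801 at different doses on change in hormones compared to placebo including" a list of analytes. The next objective reads "Changes in the number night-time awakenings (NTA" and names no comparator. Bone markers, stress markers and ECG variables are worded in the same way.

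The endpoint sections follow suit. Section 12.5.2: "The change in the number of NTAs throughout the study will be assessed". Section 12.5.3: "The change from Baseline to Week 2 in catecholamines, vasopressin, gonadotropins, prolactin, and insulin". Section 12.5.4: "The change from Baseline in bone density makers, including BSAP, osteocalcin, CTX, and P1NP will be summarized". Section 12.5.5 lists change in ECG variables and its relationship with plasma exposure, again without a comparator. Section 12.5.1 gives hormones summary statistics of change relative to baseline, also without a placebo contrast.

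On method, Section 12.6.4 says "The exploratory analyses will include summary statistics". For QT, Section 11.3.6 says "Graphical representations between ECG variables (e.g., QTcF) and plasma concentrations of ACER-801 and its metabolite will be generated", and the endpoint table in the synopsis also calls for a graphical assessment. Section 12.6.2 adds mean, SD, median, minimum and maximum for ECG data. Section 12 defers detailed analyses to a SAP to be approved before database lock and unblinding.

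**The concern.** The trial randomises 1:1:1:1 to three doses and placebo (Section 6.4). The exploratory analyses as written do not use that comparison. A change within an active arm contains the drug effect plus anything else that changed between baseline and the later measurement.

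For NTA, one such change is large and known. Section 10 says "Subjects will record VMS, including NTA, in a continuous hot flash diary during the Screening Period (2 weeks prior to Day -1", while on-treatment NTA is recorded by women confined to the unit from Day -1 to Day 16 (Sections 6.6.1 and 10.1). Sleeping in a research unit could move NTA in either direction with no drug effect at all.

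For QTc, the study collects triplicate ECGs at the PK times, at identical clock times on Day -1, Day 1 and Day 14, with blinded core-laboratory reading and a concurrent placebo arm. A plot or a mean with SD from these data does not say what size of QTc effect is ruled out at the top dose, although the data could support such a statement.

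**Working it through.** **1. The five domains side by side**

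| Domain | Placebo named in Section 3.3? | Endpoint as planned | Where baseline is taken |
|---|---|---|---|
| Hormones | Yes | Summary statistics of change (12.5.1) | In unit, Day 1 predose (LH also Day -1) |
| NTA | No | Change over the study; no baseline or time point (12.5.2) | Not defined; Section 10 implies the screening diary, before admission |
| Stress markers | No | Change to Week 2 (12.5.3) | In unit, Day 1 predose |
| Bone markers | No | Change, summarised (12.5.4) | In unit, Day 1 predose |
| ECG | No | Change; graphs against exposure (12.5.5, 11.3.6); descriptive summaries (12.6.2) | In unit, Day -1 |

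Baseline timing is from Table 1 and Sections 7.2 and 7.4. No row has an active-minus-placebo estimate, a model or an interval. The home-to-unit move can affect only the NTA row.

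**2. Why the placebo difference helps**

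Mean change in an active arm = drug effect + setting + drift. Mean change on placebo = setting + drift. The difference is the drug effect, provided setting and drift act alike in all arms, which randomisation makes reasonable.

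**3. How far a common shift could mislead (illustration)**

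Assume no drug effect and a shift of s SDs of change in every arm. The chance that a within-arm 95% CI excludes zero is a noncentral t probability with n − 1 df and noncentrality s√n. Critical values are 2.262 (n = 10) and 2.160 (n = 14).

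| Assumed s | n = 10: s√n | Chance | n = 14: s√n | Chance |
|---|---|---|---|---|
| 0.3 | 0.95 | 14% | 1.12 | 18% |
| 0.5 | 1.58 | 29% | 1.87 | 41% |
| 0.8 | 2.53 | 62% | 2.99 | 79% |

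For the difference from placebo the shift cancels and the chance stays at 5% per contrast. The documents give no estimate of s, and they do not state that within-arm tests will be run.

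**4. Precision of a QTcF contrast**

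The plan has no figure to reproduce. Section 12.1 gives 10 to 14 per arm without an SD, effect size or power. I assume an SD of change of 6 to 12 ms.

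Two-sided 90% half-width, top dose minus placebo at one time = t(0.95, 2n − 2) × SD × √(2/n).

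- n = 10: 1.734 × 0.447 × SD = 4.7 ms (SD 6) to 9.3 ms (SD 12).
- n = 14: 1.706 × 0.378 × SD = 3.9 ms (SD 6) to 7.7 ms (SD 12).

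Within-arm half-widths, t(0.95, n − 1) × SD/√n, are 3.5 to 7.0 ms (n = 10) and 2.8 to 5.7 ms (n = 14). The placebo contrast is therefore about a third wider (4.7/3.5 = 1.34).

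**5. A concentration model**

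This uses all four arms and the 13 PK times on each of Days 1 and 14 (Section 9.1). Assume a between-subject SD of 5 ms and a residual SD of 7 ms, so the single-time SD is √(25 + 49) = 8.6 ms. The single-time half-width is then 1.734 × 0.447 × 8.6 = 6.7 ms (n = 10) or 1.706 × 0.378 × 8.6 = 5.5 ms (n = 14). Under the same SDs, a mixed model on concentration gives roughly 2.5 to 4.5 ms at the top-dose Cmax. The upper end needs large between-subject variation in slope. This range also depends on the assumed concentration profile and is only indicative.

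**6. Estimates, not tests**

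At 80% power and two-sided 0.05, the detectable difference is 1.33 SD (n = 10) or 1.11 SD (n = 14) by the t distribution. A non-significant test would say little, so intervals are the useful output.

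**The case against.** Section 12 leaves the specific analyses to a later SAP, and Section 12.6.4 says what the exploratory analyses will include, which does not exclude more. With a placebo arm, readers can set the by-arm summaries beside each other. The endpoints are exploratory in a small Phase 2a study, and no objective requires a given QTc effect to be excluded. All of this stands, and it limits the weight of the point. It does not supply the estimate: by-eye comparison of arms gives neither a difference nor an interval, and the only methods named are the weaker ones.

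A reader might infer four stronger things that the documents do not support:

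- That hormones receive a placebo comparison denied to the rest. The difference is in the objective's wording only; Section 12.5.1 plans no contrast either.
- That confinement distorts every domain. Hormone, bone-marker, stress-marker and ECG baselines are all taken after admission, so only drift and procedure effects within the stay can apply there. Even for NTA, the pre-admission baseline is implied and not stated, and the diary also runs in the unit on Day -1.
- That the ECG data yield nothing but plots. Section 12.6.2 adds descriptive summaries, and Section 12.5.6 says exposure-response for QT will be assessed without naming a method.
- That the comparison will be absent from the final analysis. The text shows only that it is not specified here.

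**Conclusion.** The point holds in a limited form. No active-minus-placebo estimate or interval is stated for any of the five exploratory domains, and nothing planned gives a bound on the QTc effect. Confounding by the change of setting is specific to NTA and conditional on its baseline being the screening diary. For the other domains the reason to correct for placebo is drift and procedure effects during the stay, whose size is unknown.

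The QTcF figures rest on assumed SDs: about 4 to 9 ms half-width for a single-time contrast, and less with a concentration model if a linear relationship is adequate. They show that a useful bound can be had from the planned data, but they do not forecast this trial's precision. The change is worth making because it is cheap, but it does not affect the main PK and safety objectives' design.

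**What to change.** Write the following into the SAP before unblinding, and align the wording of Sections 3.3 and 12.5.1 to 12.5.5.

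- For all five domains, hormones included, report each dose's difference from placebo in change from a defined baseline, with a 95% CI, as estimates and not as tests.
- Define the NTA baseline as the screening diary, and name the on-treatment periods to be compared with it.
- For QTcF, keep the planned graphs and add a linear mixed model of change from time-matched Day -1 on plasma concentration. Set placebo at zero concentration, include time effects and a random subject intercept, and add a random slope if it can be estimated. Report the placebo-corrected effect with a 90% CI at each dose's geometric mean Cmax.

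The cost is SAP text and programming, with no new subjects, visits or samples. There are two downsides. The placebo-corrected intervals are wider than within-arm ones, and the model assumes an approximately linear concentration effect, which the planned plots can check.

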12.5.3 Assessment of Changes in Blood Markers Associated with Stress

- The change from Baseline to Week 2 in catecholamines, vasopressin, gonadotropins, prolactin, and insulin.

12.5.4 Markers of Bone Density

- The change from Baseline in bone density makers, including BSAP, osteocalcin, CTX, and P1NP will be summarized.

12.5.5 ECG

- The change in ECG variables (heart rate, RR, PR, QRS, QT, QTcF, and QTcB) will be assessed.
- Relationship between plasma exposure and changes in ECG variables

12.5.6 Exposure-Response Relationships

- Exploratory exposure-response relationships for efficacy (e.g., VMS), QT, and potentially safety relative to the plasma exposure of ACER-801 and its metabolite will be assessed.

12.6 Statistical Analyses

12.6.1 Pharmacokinetic Analyses

Noncompartmental analysis (NCA) will be performed for the plasma concentrations of ACER-801 and its metabolite. Summary statistics for the PK parameters (C_{max} , T_{max} , AUC_{last} ,

AUC_{inf} , $AUC\tau$, $AR_{C_{max}}$, AR_{AUC} , $MR_{C_{max}}$, MR_{AUC} , $t_{1/2}$) will be determined for ACER-801 and its metabolite for the different dosing groups.

12.6.2 Safety Analyses

All AEs/SAEs will be coded using the current version of the Medical Dictionary for Regulatory Activities to assign system organ class and preferred term classification, based on the original terms entered on the electronic case report form. The incidence of AEs will be summarized by system organ class, preferred term, relationship to study treatment, and severity for each study treatment. All AEs, including AEs that lead to premature discontinuation from the study and from study treatment and SAEs, will be recorded.

All other safety measures including laboratory tests, vital signs, concomitant medication, medical history, physical examination, and ECG data will also be summarized descriptively (mean, standard deviation, median, minimum, and maximum). Laboratory tests will also be summarized by absolute and percent change from baseline and listed by clinical significance.

Concomitant medications will be coded using the most recent version of World Health Organization Drug Dictionary.

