2.2 Safety Data

To date, no studies have been conducted with ACER-801 in subjects with iVMS.

Safety data are summarized for completed clinical studies conducted with osanetant by Sanofi. These studies were conducted in healthy subjects and patients with schizophrenia, major depressive disorder, Parkinson's disease, panic disorder, and asthma.

Osanetant was evaluated in 23 completed Phase 1 and Phase 2 studies. In single- and repeat-dose Phase 1 studies, approximately 400 subjects were exposed to doses ranging from 5 mg to 1000 mg in single dose studies and from 5 mg to 1000 mg (500 mg twice daily [BID]) in repeat-dose studies in which subjects received osanetant for up to 21 days.

In the 7 completed Phase 2 studies, a total of 821 patients were exposed to osanetant, including patients with depression (up to 200 mg QD for 6 weeks), patients with panic disorder (200 mg QD for 4 weeks), patients with schizophrenia (200 mg QD for 16 weeks), patients with asthma (200 mg QD for 6 weeks), and patients with Parkinson's disease (100 or 200 mg QD for 9 days).

Data from these studies demonstrated no major safety concerns after single-dose and repeat-dose administration up to 400 mg QD in healthy subjects, and 200 mg QD in the patient population. In controlled clinical trials, there is no evidence to date for liver function test abnormalities or weight loss, as noted in the toxicology studies.

The incidence of adverse events (AEs) was similar in the osanetant and placebo groups in completed Phase 1 and 2 trials. In patients, the serious adverse events (SAEs) reported in the osanetant group were mainly related to the condition being treated. Adverse events most frequently reported in osanetant-treated patients were headache, nausea, dyspepsia, insomnia, dizziness, and abdominal pain. These incidences were comparable in the osanetant and placebo groups.

Additional details can be found in the Investigator's Brochure.

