5.6 Study Termination Criteria

The Sponsor or designee will review pooled and individual subject data during the course of the study. A single occurrence of the following safety events will trigger an ad hoc meeting to review individual cases:

- Hepatic toxicity such as marked elevations in transaminases or simultaneous elevations in hepatic transaminases and bilirubin (i.e., Hy's Law)
- Severe renal impairment
- Severe cardiovascular dysfunction such as arrhythmia or other abnormalities as indicated by ECG readings

If the Sponsor or its designee determines that the event is drug-related and a clear safety signal has been identified, early termination of the study may occur.

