11.3.7 Clinical Laboratory Tests

Hematology and coagulation; serum chemistry; urinalysis; urine screening for drugs of abuse, cotinine, and alcohol will be performed for each subject as indicated in Table 1 and [Table 5](#). Clinical laboratory tests may be repeated once for subjects who had previous clinical laboratory test results that revealed clinically significant abnormalities per the investigator's request. Pregnancy tests may be reported in the event of any positive or equivocal test result. If a pregnancy test is positive, Acer must be notified, and the subject will be followed as outlined in [Section 11.2.6](#), until pregnancy outcome. Additional tests may be performed at other times, if deemed necessary. Blood samples may also be used for the assessment of tachykinin peptides, including NKB, NKA, and substance P.

Virology testing will include testing for the presence of HIV antibody, HbsAg, and HCV as indicated in Table 1. Blood samples will be appropriately processed, and laboratory reports will be made available to the investigator in a timely manner to ensure appropriate clinical review and subject inclusion/exclusion based upon results. Procedures for handling and shipping of all laboratory samples will be included in a laboratory manual provided by the central laboratory facility.

All clinical laboratory tests will be performed at the clinical unit) (instructions in the Study Reference Manual and Laboratory Manual).

Abnormalities in clinical laboratory tests that are considered clinically significant by the investigator will be considered Aes and recorded on the AE eCRF. In addition, ALT and AST elevations greater than 5 times the upper limit of normal (i.e., Grade 3 or higher based on CTCAE) will be considered clinically significant for the purposes of this study and reported as Aes.

Any clinically significant abnormal clinical laboratory test results, including test results obtained through Day 16/ET, will be repeated. For any repeat analysis, the abnormal value will be followed regularly until: (1) the value returns to screening or Day -1 values or within normal range; (2) a valid reason, other than Aes related to the study drug, is identified; or (3) the investigator determines that the abnormal value is no longer clinically significant or that further follow-up is no longer deemed medically necessary.

The list of clinical laboratory tests and other analytes to be tested is provided in Table 5.

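### No planned analysis counts women per arm by ULN multiple or pairs ALT/AST with bilirubin, so elevations up to 5 × ULN without discontinuation are counted only on investigator judgement

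*Combined protocol and SAP*

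**What the plan says.** Section 12.6.2 has laboratory tests "summarized descriptively (mean, standard deviation, median, minimum, and maximum"), followed by "Laboratory tests will also be summarized by absolute and percent change from baseline and listed by clinical significance". AE incidence is tabulated by treatment and severity. The primary laboratory safety endpoint in 12.3.2 is "Clinically significant changes in clinical laboratory evaluations" over the two-week treatment period, and SAEs and discontinuations are a separate primary safety endpoint.

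Section 11.3.7 fixes one numeric rule: "ALT and AST elevations greater than 5 times the upper limit of normal (i.e., Grade 3 or higher based on CTCAE") count as clinically significant and are reported as AEs. At or below that level, a laboratory abnormality becomes an AE only if the investigator considers it clinically significant.

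Elsewhere the protocol treats liver safety woman by woman. Both laboratory criteria in 5.5 combine an ALT/AST multiple of ULN with total bilirubin. In 5.6 a single case of "Hepatic toxicity such as marked elevations in transaminases or simultaneous elevations in hepatic transaminases and bilirubin (i.e., Hy's Law") triggers a review meeting. Exclusions 1b and 2 and the ban on hepatotoxic drugs in 5.3.2 are also liver-based. On prior data, section 2.2 says of the controlled clinical trials that "there is no evidence to date for liver function test abnormalities or weight loss, as noted in the toxicology studies".

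**The concern.** A drug effect on the liver typically shows in a few individuals rather than as a shift of the whole arm. The informative quantities are then how many women crossed each multiple of ULN, and whether ALT/AST and bilirubin rose together in the same woman. The protocol uses such quantities to stop dosing and to trigger review, but plans no tabulation of them by arm.

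At stake is how well the primary safety objective is answered across doses. Elevations that fall short of the automatic rule could differ between 200 mg BID and placebo, and the report would have no count from which to see it unless the investigator had flagged each one.

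**Working it through.** **Which elevations are counted by arm.** Setting 5.5, 5.6, 11.3.7, 12.3.2 and 12.6.2 side by side:

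- ALT/AST above 5 × ULN: automatically an AE, so in the AE table by arm.
- Up to 5 × ULN, with a 5.5 criterion met during dosing: drug is withdrawn and the woman counts as a discontinuation, though not in a liver-test category.
- Up to 5 × ULN, no discontinuation, called clinically significant: an AE and in the listing, so counted.
- Up to 5 × ULN, no discontinuation, not called clinically significant: no count. The value enters the maximum, SD, mean and change summaries only.
- A joint ALT/AST and bilirubin rise first seen after the last dose, for example on Day 16: there is no dosing left to stop, so it is counted only if it is above 5 × ULN or called clinically significant.

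The 5.6 meeting reviews individual cases and produces no table by arm.

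**What the planned summaries would show.** The plan states no liver figure to reproduce. Inputs:

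- n = 10 to 14 per arm (12.1).
- Assumption, not in the documents: every woman starts at b = 0.5 × ULN, one rises to x = 4 × ULN, and the others do not change.

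Mean = ((n − 1)b + x)/n. Mean percent change = 100 × (x − b)/(b × n), where 100 × (4 − 0.5)/0.5 = 700%.

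| Summary | n = 10 | n = 14 |
|---|---|---|
| Mean (× ULN) | (9 × 0.5 + 4)/10 = 0.85 | (13 × 0.5 + 4)/14 = 0.75 |
| Median (× ULN) | 0.5 | 0.5 |
| Maximum (× ULN) | 4 | 4 |
| Mean percent change | 700/10 = +70% | 700/14 = +50% |
| Median percent change | 0% | 0% |
| Share of the arm in a count table | 1/10 = 10% | 1/14 = 7.1% |

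**Sensitivity to the assumption.** Over b = 0.4 to 0.8 and x = 3 to 5, the median never moves and mean percent change runs from +20% to +115%. The mean stays at or below 1 × ULN only while b ≤ (n − x)/(n − 1). For x = 5 that is b ≤ 0.56 (n = 10) or 0.69 (n = 14). For x = 3 it is 0.78 or 0.85. At b = 0.7, x = 5 and n = 10 the mean is (9 × 0.7 + 5)/10 = 1.13.

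**Two women at 4 × ULN, b = 0.5.** The mean is (8 × 0.5 + 8)/10 = 1.2 or (12 × 0.5 + 8)/14 = 1.0, and the maximum is still 4.

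**What remains hidden.** With n = 14, the mean change of 3.5/14 = 0.25 × ULN arises from any set of rises and falls that sums to 3.5 × ULN. Neither it nor the maximum gives a count, and neither links to the same woman's bilirubin.

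**The case against.** The strongest reply is that the plan already shows more than a group average. That is right, and it rules out several stronger readings.

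- A reader might infer that liver tests are summarized by means and medians alone. They are not: the maximum, the listing, the AE tables and the discontinuation endpoint are all planned.
- A reader might infer that every summary stays normal when one woman is affected. Mean percent change does not, and the mean itself can pass 1 × ULN with a higher baseline or a second case.
- A reader might infer that summaries by scheduled visit would miss repeat draws. No section limits the summaries to scheduled visits. The text does not say how repeat and Day 16 values enter.
- A reader might call liver injury the main known risk and expect the safety objective to be answered wrongly. Section 2.2 points to toxicology studies and reports no such evidence in controlled trials, the protocol does not rank harms, and 5.6 lists renal and cardiovascular events beside hepatic ones.

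The reply adds that graphs of potential safety signals against exposure are planned (12.5.6), and that section 12 defers detail to a statistical analysis plan due before database lock. Such displays are ordinary content for that plan, and their absence here does not prove they will be omitted. But section 12.6.2 does state a laboratory method, the supplied text contains no such table, and a general exposure graph is not a per-arm count.

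**Conclusion.** The point holds as a gap in tabulation. Nothing in the supplied text counts women per arm by ULN multiple, shows a categorical shift from baseline, or displays ALT/AST and bilirubin jointly. The affected group is narrow: mainly ALT/AST elevations up to 5 × ULN that lead to no discontinuation and are not called clinically significant, including joint rises first seen after dosing ends. One such woman is 7.1% to 10% of an arm. She would leave a trace in the maximum, the mean and mean percent change, but no count and no link to her bilirubin.

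The means rest on the assumed 0.5 × ULN baseline; the finding about missing counts does not. The added table would describe the data and would not create sensitivity. At an assumed true rate of 5%, the chance of at least one case in an arm is 1 − 0.95^10 = 40% or 1 − 0.95^14 = 51%, so an empty row would be weak reassurance. This is a worthwhile, inexpensive improvement, not a flaw that invalidates the safety analysis.

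**What to change.** In 12.6.2 and the statistical analysis plan, add:

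- A table by arm, including placebo, of each woman's worst ALT, AST and total bilirubin after the first dose, using scheduled, repeat and Day 16/ET values. Categorize by ULN multiple, for example above 1, 2, 3 and 5 × for ALT/AST and above 1 and 2 × for bilirubin.
- A shift from baseline to worst category. Exclusion 1b admits women with ALT/AST up to 2 × ULN and exempts Gilbert's Syndrome from the bilirubin limit, so a worst value needs its baseline.
- A per-subject plot of peak ALT/AST against peak bilirubin.
- A statement that these counts do not depend on the clinical-significance call.

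Section 5.5 writes the multiple before the inequality sign. The sponsor should clarify that notation so that the tabulated categories match the criteria as intended.

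The cost is one table with its shift display and one figure, from data already collected. No test is added and no clinical rule changes. Some non-specific mild elevations will appear, and the placebo column puts them in context.
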